7.1 Sample Size Determination and Statistical Methods

For Aim1 (To assess the efficacy of megestrol as part of the 24 week iKanEat protocol), if at least 90% of the treatment group successfully transitions (in pilot 100% successfully transitioned), with 72 participants, we would have .80 power to detect an odds ratio of .21. With 60 participants, we would have power to detect an odds ratio of .18. If only 75% of the treatment group successfully transitions, we will still have .80 power to detect an odds ratio of .25 with our smallest expected sample size of 60.

For Aim 2 (To assess the safety of megestrol as part of the 24 week iKanEat protocol), all analyses are descriptive, so a power analysis is not conducted.

For Aim 3 (To examine the effect of the transition from tube to oral feeding on parent stress and parent and child quality of life), with 60 participants, we would have .78 power to detect differences in slopes over the four data points equivalent to a standardized effect size of $d=.75$ or larger. With a sample size of 72, there will be .80 power to detect a difference in slopes equivalent to a standardized effect size of .70. To answer those questions in which the grouping factor is success in treatment, such as 3A (The transition to oral feeding will temporarily increase parent stress at week 14 at the cessation of tube feeding, with a return to baseline by week 24) and 3B (The transition to oral feeding will increase parent/child quality of life at 24 weeks compared to week 0), assuming that 60% of the participants across groups are successful, we would have sufficient power to detect effects equivalent to a standardized effect size of $d=.42$ or larger. With a sample size of 60, the minimum detectable effect size would increase to $d=.59$. If 70% percent are successful, with 72 participants we can detect effects equivalent to $d=.61$, and with 60 participants $d=.70$. These are moderate sized effects.

Planned Analyses

CONFIDENTIAL

This material is strictly confidential and is intended solely for the guidance of clinical investigation. Do not disclose or use except as authorized in writing by the study sponsor

To address Aim 1, analyses will be conducted using Generalized Linear Mixed Models with a logit link within SAS Proc GLIMMIX to model the binary outcome of transitioned to oral feeding (y/n) defined as at least 90 percent of calories consumed orally. Fixed effects (dummy variables) will be entered for each site as described by McNeish and Stapleton (2016) to account for the clustering of the participants within sites. This will result in essentially, a logistic regression model with appropriate standard errors. Sex, age at initiation, treatment condition, and interactions with treatment condition will enable us to examine the effect of group assignment on successful transition to oral feeding by week 24. Interactions between treatment group and sex will be examined but will not be sufficiently powered to reach definitive conclusions about sex differences. In addition to overall effects, subgroup analyses will be reported for males and females to examine treatment effects within sex groups.

To address Aim 2, we will determine whether any of our participants in either group have adrenal sufficiency levels outside of the normal range at any time point. Should any participant have levels outside of the normal range, we will descriptively examine the individual characteristics associated with this, including group assignment, medical diagnoses, sex, and age at initiation. These characteristics will be reported descriptively.

To address Aim 3, we will model parent stress levels, child quality of life, and parent quality of life for participants in both treatment conditions over the four measurement occasions using General Linear Mixed Models. As in Aim 1, fixed effects for site will be added to the model as will sex and age at initiation. Once the shape of the trajectory over time has been modeled, a successful transition to oral feeding indicator, defined as consuming 90% or more of calories orally, will be added to the model at level 2. For 3A, the primary variable of interest will be the time by successful transition interaction on parental stress level. Estimate statements will examine group differences in stress at week 14 and 24. To address hypothesis 3B regarding Quality of Life outcomes, we will initially model the trajectory over time for each outcome with the same set of predictors as in 3A. Of primary interest will be the time by successful transition interaction on subscales for parental quality of life and the parent impact time, general health perceptions, growth and development, and parent impact emotional subscales for child quality of life which showed the greatest response to intervention in our pilot data. It is expected that some subscales such as general health perceptions and parent impact time will show more response to intervention than others. A significant positive slope for some quality of life indicators are hypothesized for those children who transition to oral feeding while stable or declining quality of life ratings are expected for those who are unable to transition to oral feeding. Finally, to complete our analyses of sex as a biological variable (SABV) we will assess study outcomes by gender.

To address Aim 4, the Shannon Index⁶⁰ will be used to determine microbial diversity. Data analysis will be completed using the paired t-test unless the data is not normally distributed in which case analysis will be completed with the Wilcoxon Signed Rank test to compare the index values of patients on each diet.

Heterogeneity of Subjects

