1.3 Review of Literature

Feeding

Our team has published several studies of pediatric feeding difficulties. Our early work examined the relationship between feeding difficulties and medical complexity (27), and found that by the time of introduction of solid food, preterm children more often demonstrated difficulty than full-term children. Also, medical factors, primarily the need for breathing assistance, accounted for more of the variance in this relationship than prematurity alone. We have also assessed parent perceptions of mealtime behaviors in children who are tube fed, and learned that parents report surprisingly high levels of stress around the mealtime, both for themselves and their children (28). We have also examined pediatric sensory processing issues related to feeding problems (29) and found that 67% of children who present for treatment have sensory profile scores in the abnormal range. Also, co-occurring diagnoses are frequent in the areas of developmental, gastrointestinal, and neurological areas. This foundational work led to the multidisciplinary protocol which we call iKanEat that was designed to move these complicated children to oral eating on an outpatient basis.

Clinical Data: iKanEat

In 2008, our team published a retrospective chart review of the first 9 patients to undergo our iKanEat tube weaning protocol clinically (30). At that time, the protocol included two medications (amitriptyline and megestrol) as well as behavioral and oral motor/sensory components. Results from this initial retrospective study indicated that the nine initial patients were 100% orally fed at the end of the intervention period, and 8 of the 9 were 100% orally fed six months later (one patient with cerebral palsy had stamina issues and was only able to sustain 50% of intake orally over the long term). This pilot work led us to NIH funding to conduct a randomized controlled trial of amitriptyline, one of the two medications in the protocol (HD066629). The findings (11) suggest that 100% of children who completed the protocol moved from tube feeding to total oral feeding, regardless of group assignment (amitriptyline, placebo). More specifically, of the children who completed the 6 month protocol, % kilocalories/day obtained orally (our primary outcome measure) increased statistically significantly from $M = 31.51\%$ ($SD = 16.09\%$) to 100%. Therefore, it does not appear that amitriptyline is a necessary component of the iKanEat protocol.

Parent Stress

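### Section 7.1 gives the 3A/3B detectable effects only at 60% and 70% success, which leaves out Aim 1's lead scenario (about 76–78%), and the four printed effects do not scale with one another

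*Combined protocol and SAP*

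**What the plan says.** All the power statements are in section 7.1.

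- **Aim 3, by success.** For 3A and 3B the grouping factor is success in treatment. The plan writes "assuming that 60% of the participants across groups are successful, we would have sufficient power to detect effects equivalent to a standardized effect size" of .42. It gives no sample size there, but the next sentence implies 72: "With a sample size of 60, the minimum detectable effect size would increase to $d=.59". It then adds "If 70% percent are successful, with 72 participants we can detect effects equivalent to $d=.61$, and with 60 participants $d=.70". It calls these effects moderate in size. The power is described only as sufficient, and no alpha, sidedness or within-subject correlation is given.
- **Aim 1, lead scenario.** "if at least 90% of the treatment group successfully transitions (in pilot 100% successfully transitioned), with 72 participants, we would have .80 power" for an odds ratio of .21. "With 60 participants, we would have power to detect an odds ratio of .18".
- **Aim 1, fallback.** "If only 75% of the treatment group successfully transitions, we will still have .80 power to detect an odds ratio of .25" at N=60.
- **Planned test.** Under Planned Analyses, Aim 3 uses general linear mixed models over four occasions, with the time-by-success interaction as the effect of main interest.
- **Background.** Section 1.3 reports of the previous trial that "100% of children who completed the protocol moved from tube feeding to total oral feeding, regardless of group assignment".

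**The concern.** A comparison of successful with unsuccessful children is limited by the smaller group. The better the intervention works, the fewer unsuccessful children there are and the weaker the 3A and 3B contrasts become. Aim 1 and Aim 3 describe the same children in the same section, so the success shares behind their power statements should correspond. Aim 3 stops at 70%, while Aim 1 opens with a scenario whose overall share is higher. If that scenario occurs, a non-significant time-by-success result on stress or quality of life would be read against a stated sensitivity that the study would not have.

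**Working it through.** **Inputs.** Aim 1 success rates and odds ratios, and Aim 3 shares and effects, from section 7.1; 1:1 allocation from section 5.3. Assumed: two-sided 5% and .80 power. The plan states neither for these effects; .80 is the figure used for most other statements in 7.1.

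**Step 1. Overall success implied by Aim 1.** Placebo odds = odds ratio × treatment odds; overall share = mean of the two arms.

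- 90%, .21, N=72: 9 × .21 = 1.89, placebo 1.89/2.89 = 65.4%. Overall (90 + 65.4)/2 = 77.7%, so 72 × .223 = 16.1 unsuccessful.
- 90%, .18, N=60: 9 × .18 = 1.62, placebo 1.62/2.62 = 61.8%. Overall 75.9%, so 60 × .241 = 14.5 unsuccessful.
- 75%, .25, N=60: 3 × .25 = .75, placebo .75/1.75 = 42.9%. Overall 58.9%, so 24.6 unsuccessful.

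Aim 3's 70% case has 21.6 (N=72) or 18 (N=60) unsuccessful. At 90% overall there would be 7.2 or 6.0. Replacing Aim 1's odds ratios with those a two-sided .80 calculation gives (.184 and .161) moves the lead-scenario shares only to 75–76%.

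**Step 2. Try to reproduce the printed effects.** As a single-occasion two-sample t-test at .80 power, the detectable effects are .68 (60%, N=72), .75 (60%, N=60), .73 (70%, N=72) and .80 (70%, N=60). The plan prints .42, .59, .61 and .70. Repeated measures could lower the effective SD, so I asked what SD factor each printed figure needs: d / (2.80 × √(1/n₁ + 1/n₂)). The answers are .62, .80, .85 and .89. No common factor fits all four.

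**Step 3. Scaling among the printed effects.** With the same test and power, d is proportional to 1/√(N·p(1−p)), where p is the success share.

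- N=72 to 60 at 60%: expected √(72/60) = 1.095; printed .59/.42 = 1.40.
- 60% to 70% at N=72: expected √(.24/.21) = 1.07; printed .61/.42 = 1.45.
- N=72 to 60 at 70%: expected 1.095; printed .70/.61 = 1.15.

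The .42 is furthest out of line.

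**Step 4. Carry the printed effects to Aim 1's lead shares.** Grant each effect exactly .80 power at its own share. Ratio r = √[p₀(1−p₀) / p₁(1−p₁)], new detectable effect = d × r, power at the printed d = Φ(2.80/r − 1.96).

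| Printed d | Own share, N | Lead share | r | Power at printed d | Detectable d |
|---|---|---|---|---|---|
| .42 | 60%, 72 | 77.7% | 1.18 | .66 | .49 |
| .59 | 60%, 60 | 75.9% | 1.15 | .69 | .68 |
| .61 | 70%, 72 | 77.7% | 1.10 | .72 | .67 |
| .70 | 70%, 60 | 75.9% | 1.07 | .74 | .75 |

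A one-sided 5% calibration gives .68, .70, .73 and .75.

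At 90% overall, r = √(.24/.09) = 1.63 for the 60% cases and √(.21/.09) = 1.53 for the 70% cases. Power is then about .40 and .45, and the detectable effects run from .42 × 1.63 = .69 to .70 × 1.53 = 1.07.

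**The case against.** The Aim 3 statements are conditional on 60% or 70% success, and another scenario does not falsify a conditional statement. The 76–78% is not a rate the plan assumes either: it joins an assumed 90% to a minimum detectable odds ratio. Aim 1's fallback gives 59%, so Aim 1 spans about 59–78% and Aim 3's range lies almost wholly inside it. All of this stands. A reader might infer that Aim 3 contradicts Aim 1, or that the printed effects fail a claimed power. The documents support neither: the fallback matches the 60% case, and no numeric power is claimed. What remains is a gap at the upper end. With 90% on megestrol, an overall share of 70% needs placebo success of 50%, an odds ratio of 1/9 = .11, which is a larger effect than Aim 1 is sized to detect. A weaker megestrol effect raises the share further.

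A reader might also infer that only large effects are detectable under the lead scenario. That rests on a single-occasion t-test (about .80 at N=72 and .86 at N=60), whereas the plan uses a mixed model over four occasions with no stated correlation. Carrying the printed effects forward gives .49–.75.

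The previous trial's 100% concerns completers only, so it does not show that there will be no comparison group; section 1.3 also reports withdrawals there. The plan does not say how children without a week 24 outcome are classed. If the 12 lost between 72 and 60 counted as unsuccessful, the N=60 lead scenario would give 45.5/72 = 63%, inside Aim 3's range. That is a reason to state the classification, not evidence that 60–70% was derived that way.

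Finally, Step 4 treats four mutually inconsistent figures as each correct. It is a concession to the plan that isolates the effect of the share, and does not estimate actual power.

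**Conclusion.** The concern holds as a gap in coverage plus a need to recheck. The 3A/3B detectable effects are stated for success shares that include Aim 1's fallback but not its lead scenario, where about 16 (N=72) or 14–15 (N=60) children would be unsuccessful. Granting .80 power at the printed shares, power at the printed effects falls to about .66–.74, and to about .45 or lower if about 90% succeed overall. The 90% case is a sensitivity case, not a planning input.

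Separately, the four printed effects cannot all come from one test at one power with one SD factor. That does not depend on the value of the within-subject correlation, provided it is the same in all four cells. Absolute power does depend on it, so the documents do not establish that the printed effects are underpowered at their own 60% and 70% shares.

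Nor do they support striking out the description of the effects as moderate in every case, or recasting 3A and 3B as estimation only. The matter concerns a secondary aim and leaves Aim 1 untouched.

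**What to change.** In section 7.1, recalculate the 3A/3B detectable effects for the planned time-by-success contrast. State alpha, sidedness, power and the assumed within-subject correlation.

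Do this at the shares Aim 1 implies: about 59% (75% on megestrol, odds ratio .25), 76% (90%, .18, N=60) and 78% (90%, .21, N=72), with 90% as a sensitivity case. Give the expected number of unsuccessful children beside each. Recheck all four printed figures in the process, starting with .42. Keep the description of the effects as moderate only where the recalculated value supports it. The t-test values above should not be inserted as final, because they are not for the planned model.

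The cost is one small recalculation and a few sentences, with no extra patients or procedures. The downside is less favourable stated detectable effects for a secondary aim.

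### Aim 3's four detectable effects by transition success (.42, .59, .61, .70) cannot come from one two-group calculation, and Hypothesis 3A's change from week 0 has no named contrast

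*Combined protocol and SAP*

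**What the plan says.** All of this is in section 7.1 of the combined protocol and SAP unless noted.

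**Detectable effects by transition success.** Assuming 60% of children succeed, the plan claims "sufficient power to detect effects equivalent to a standardized effect size of $d=.42$ or larger". No sample size is attached to that figure, but the next sentence implies 72: "With a sample size of 60, the minimum detectable effect size would increase to $d=.59". It continues: "If 70% percent are successful, with 72 participants we can detect effects equivalent to $d=.61$, and with 60 participants $d=.70". It sums up: "These are moderate sized effects". No test, alpha, numerical power or within-person correlation is given for these four values.

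**Slope figures in the same paragraph.** With 60 participants, "we would have .78 power to detect differences in slopes over the four data points" at an effect of .75. With 72, "there will be .80 power to detect a difference in slopes equivalent to a standardized effect size of .70".

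**Hypothesis 3A.** Section 2 (Aim 3) predicts that parent stress goes up at week 14, when tube feeding stops, and is back at its starting level by week 24. The planned analysis fits a mixed model over four occasions: "Once the shape of the trajectory over time has been modeled, a successful transition to oral feeding indicator" is then added. For 3A, "the primary variable of interest will be the time by successful transition interaction on parental stress level", and ESTIMATE statements compare the two groups at weeks 14 and 24. Section 3.3 lists parent stress and quality of life as secondary endpoints.

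**The concern.** In a two-group comparison the detectable effect depends on the group sizes through one known factor. Losing a sixth of the sample (72 to 60) should cost about 10% in detectable effect, yet the plan shows a 40% increase at 60% success and 15% at 70% success. The order is also wrong: .61 (72 children, 70:30) exceeds .59 (60 children, 60:40), where a two-group test gives the reverse.

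A null result on stress or quality of life would be read against these figures. If the trial cannot reliably detect .42, such a null would be over-interpreted.

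The second gap is in the match between hypothesis and analysis. Hypothesis 3A concerns change from week 0, but the comparisons named for it contrast children who transition with children who do not. If stress rises equally in both groups from equal week 0 levels, all of those comparisons are null although stress rose. If the groups already differ at week 0 and nothing changes, the week 14 and week 24 level differences can be non-zero although stress did not rise.

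**Working it through.** **Inputs from section 7.1.** Totals of 72 and 60; success shares of 60% and 70%. Group sizes (success vs failure): 43.2 vs 28.8, 36 vs 24, 50.4 vs 21.6, 42 vs 18.

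**Assumed, not in the documents.** Two-sided alpha .05; power .80 for the four values; equal groups for the slope figures; a two-occasion change score as a proxy for the four-occasion mixed model; within-person correlation ρ from .5 to .8.

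**Step 1. The slope pair is coherent.** With a noncentral t and equal groups, find the multiplier on d that returns the stated power. For (.75, 30 vs 30, power .78) it is .957. For (.70, 36 vs 36, power .80) it is also .957. One calculation explains both.

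**Step 2. The four values by success are not.** For one two-group test, K = d / √(1/n₁ + 1/n₂) must be essentially the same in every cell, because alpha, power and any common variance or repeated-measures factor cancel.

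| Cell | Stated d | √(1/n₁+1/n₂) | K, allowing for rounding of d |
|---|---|---|---|
| 72, 60% | .42 | .2406 | 1.73–1.77 |
| 60, 60% | .59 | .2635 | 2.22–2.26 |
| 72, 70% | .61 | .2572 | 2.35–2.39 |
| 60, 70% | .70 | .2817 | 2.47–2.50 |

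No two ranges overlap. Dropping .42, the one value whose sample size is inferred, does not help, because the other three are already disjoint. If .59 at 60 children is kept, .42 needs 60 × (.59/.42)² ≈ 118 children.

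**Step 3. Ratios to the first cell.** Expected (noncentral t): 1.10, 1.07, 1.17. Stated: .59/.42 = 1.40, .61/.42 = 1.45, .70/.42 = 1.67. Over alpha .01 to .20 and power .70 to .90, the expected ratios stay within 1.097–1.101, 1.069 and 1.173–1.177.

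**Step 4. What one calculation gives.** Change-score value = plain value × √(2(1−ρ)).

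| | 72, 60% | 60, 60% | 72, 70% | 60, 70% |
|---|---|---|---|---|
| Stated | .42 | .59 | .61 | .70 |
| Plain test (same as ρ = .5) | .68 | .75 | .73 | .80 |
| ρ = .6 | .61 | .67 | .65 | .72 |
| ρ = .7 | .53 | .58 | .57 | .62 |
| ρ = .8 | .43 | .48 | .46 | .51 |
| ρ needed for the stated value | .81 | .69 | .65 | .62 |

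Power for .42 at 72 children and 60% success is .41, .49, .60 and .78 at ρ = .5, .6, .7 and .8. At ρ = .8, where .42 nearly works, the other three stated values would have power .94, .96 and .97.

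**Step 5. Hypothesis 3A, 36 vs 24 children** (60% of 60; effects in SD units, assumed).

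- *No rise, but a persisting week 0 difference of 0.3 or 0.5 SD:* the week 14 level contrast rejects with probability .20 or .46.
- *A shared 0.5 SD rise from equal week 0 levels:* the named comparisons reject at the alpha rate only. A paired week 14 minus week 0 test in the 36 transitioning children, with effect 0.5/√(2(1−ρ)), has power .83, .90, .96 and above .99 at ρ = .5 to .8.
- *Return to baseline:* the 95% confidence interval half-width for week 24 minus week 0 in those 36 is t(.975, 35) × √(2(1−ρ))/√36 = .34, .30, .26 and .21 SD.

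**The case against.** **The figures may not come from a two-group test.** The plan names no test, and 3A and 3B are worded as changes over time. A one-sample paired t test at two-sided .05 comes close to all four values if the group is allowed to change: .42 in 43 successes has power .77, and .59, .61 and .70 in 24, 22 and 18 failures have power .79, .78 and .80. On that reading .42 is the odd one out, because in 29 failures it has power only .59. This is a fair reconstruction and a reason not to declare which figure is wrong. It does not rescue the paragraph: the text says success is the grouping factor, and the reconstruction has to switch from successes to failures after the first value.

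**Power may differ by cell.** The slope figures do use .78 and .80. The spread needed here is far wider. At ρ = .69, where .59 has power .80, .42 has about .59 and .70 about .87.

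**The correlation may be irrelevant.** If d is scaled by the SD of the change, ρ drops out and power for .42 is .41 throughout. That removes the favourable end of the range.

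**The model already covers 3A.** It estimates the overall trajectory before the success indicator enters, so a shared rise would show there, and the time-by-success interaction is not misled by a week 0 difference. Both points stand. The gap is in what is prespecified, and the model itself can supply the missing contrasts. Even so, neither the trajectory step nor the interaction is a stated test of a rise and return in children who transition.

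**It is a secondary aim.** True. Nothing shows that these figures set the sample size, and the primary inference is unaffected.

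**Conclusion.** Both points hold. The inconsistency among the four detectable effects follows from the stated numbers alone: it needs no assumed alpha, power or correlation, only that the four values describe one comparison by success. The value .42 lies furthest from the rest, but whether it is too small or the others too large cannot be settled from the documents. The .41 to .78 power range for .42 does rest on the assumed two-sided .05 and on ρ between .5 and .8. Calling the effects moderate is unsupported until the values are restated.

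For 3A, the named comparisons do not directly answer whether stress rose from week 0 and came back. The sizes given for that part rest on assumed effects and week 0 differences, so they are illustrations. The omission itself is plain from the text. The correction should be made, but it concerns a secondary aim and leaves the Aim 1 analysis untouched.

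**What to change.** 1. In section 7.1, recompute all four values under one stated test, alpha, sidedness and power. Attach a sample size to each, including the first, and show a range over the within-person correlation. State whether d is scaled by the raw SD or the change SD. Keep the description of the effects as moderate only if the new values support it.
2. In the Aim 3 planned analysis, add two ESTIMATE contrasts from the same mixed model for children who transition: week 14 minus week 0 and week 24 minus week 0, each with a 95% confidence interval. A non-significant week 24 difference does not by itself show a return to baseline, so the interval should be reported and interpreted.
3. Keep the time-by-success interaction as the between-group comparison.

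The cost is SAP wording and two lines of code on data already being collected, with no extra visits or participants. The stated sensitivity may come out less favourable, and there will be two more estimates to report.
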